### **6.3 SUBJECT SETS ANALYSED**

The following subject sets will be defined for statistical analysis:

- Randomised set (RS):  
This subject set includes all subjects who were randomised, i.e., who have been assigned a subject number, whether treated or not.
- Treated set (TS):  
This subject set includes all subjects who received at least one dose of study drug, as defined in Section 7.3.1 of the CTP. This is the full analysis set population in the sense of ICH-E9.
- Pharmacokinetic parameter analysis set (PKS):  
This subject set includes all subjects of the TS who provide at least one PK parameter that was not excluded due to relevant PVs or due to PK non-evaluability, as defined in Section 7.3.1 of the CTP.

All ECG analyses are performed on the TS, except for the exposure-response analyses, which are performed on the ECGPCS defined below.

- ECG PC set (ECGPCS):  
This subject set consists of all subjects in the TS who provide a baseline value and at least one post-baseline value for at least one ECG variable used in the exposure-response analysis, and a corresponding (i.e. time-matched) valid drug plasma concentration. Since placebo subjects will be included in the exposure-response analyses with plasma concentration set to 0, a plasma concentration BLQ is considered a valid drug plasma concentration for placebo subjects.

The discussion of all exceptional cases and problems and the decisions on the allocation of subjects to analysis sets will be made at latest at the RPM/DBLM.

Table 6.3: 1 Subject sets analysed

| Class of endpoint  | Subject set |    |     |        |
|--|-------------|----|-----|--------|
|  | RS          | TS | PKS | ECGPCS |
| Disposition  | X           | X  |     |        |
| Exposure   |             | X  |     |        |
| IPVs   | X           |    |     |        |
| Demographic/baseline endpoints   |             | X  |     |        |
| Primary endpoint   |             | X  |     |        |
| ECG endpoints and plasma concentrations used in exposure-response analysis |             |    |     | X      |
| ECG endpoints in other analyses  |             | X  |     |        |
| Other safety parameters  |             | X  |     |        |
| Secondary PK endpoints   |             |    | X   |        |

## 6.5 POOLING OF CENTRES

This section is not applicable because centre is not included in the statistical model.

## 6.6 HANDLING OF MISSING DATA AND OUTLIERS

The endpoint will be derived taking account for handling of missing data as defined in the CTP, Section 7.4.

**CTP:** *If a subject is removed from or withdraws from the trial prior to first administration of trial medication, the data of this subject will not be entered in the case report form (CRF) or trial database and will not be reported in the clinical trial report (CTR). The only exception to this rule is when the subject had an AESI and/or SAE that the investigator considers related to the screening procedure. If a subject is removed from or withdraws from the trial after first administration of trial medication, this will be documented and the reason for discontinuation must be recorded in the CRF. In this case, the data will be included in the CRF/trial database and will be reported in the CTR.*

Missing or incomplete AE dates are imputed according to BI standards (see 001-MCG-156\_RD-01 ([3](#))).

Missing data and outliers of PK data are handled according to BI standards (see 001-MCS-36-472\_RD-01) ([4](#)).

## **6.7 BASELINE, TIME WINDOWS AND CALCULATED VISITS**

There will be a centralised evaluation of all 12-lead ECG recordings at the time points specified in Table 6.7: 1 below:

Table 6.7: 1 Time schedule of 12-lead ECG recordings

| Visit | Day | Planned time
[hh:mm]
(relative to drug
administration) | Study phase |
|--------------|------------|---|--------------------|
| 2            | 1          | 00:15   | On-treatment       |
|              |            | 00:30   |                    |
|              |            | 00:45   |                    |
|              |            | 01:00   |                    |
|              |            | 01:30   |                    |
|              |            | 02:00   |                    |
|              |            | 04:00   |                    |
|              |            | 08:00   |                    |
|              |            | 12:00   |                    |
|              | 2          | 23:55   |                    |

Table 6.7: 1 Time schedule of 12-lead ECG recordings (continued)

| Visit | Day | Planned time
[hh:mm]
(relative to drug
administration) | Study phase  |
|-------|-----|---|--------------|
| 2     | 14  | 310:00  | On-treatment |
|       |     | 312:15  |              |
|       |     | 312:30  |              |
|       |     | 312:45  |              |
|       |     | 313:00  |              |
|       |     | 313:30  |              |
|       |     | 314:00  |              |
|       |     | 316:00  |              |
|       |     | 320:00  |              |
|       |     | 324:00  |              |
|       | 15  | 336:00  |              |
|       |     | 337:00  |              |
|       | 28  | 646:00  |              |
|       |     | 648:15  |              |
|       |     | 648:30  |              |
|       |     | 648:45  |              |
|       |     | 649:00  |              |
|       |     | 649:30  |              |
|       |     | 650:00  |              |
|       |     | 652:00  |              |
|       |     | 656:00  |              |
|       |     | 660:00  |              |
|       | 29  | 672:00  |              |

Triple ECGs (3 single ECGs recorded within 180 sec) will be recorded on all time points on Day 1, Day 2, Day 14, Day 15, Day 28 and Day 29. On all other time points, single ECGs will be recorded.

The value of an ECG variable at each of the time points with triple ECG is defined as the arithmetic mean of the 3 single ECG measurements. In particular, the baseline value of an ECG variable is defined as the mean of the triple ECG measurements prior to first drug administration.

In all other analyses (except for analyses of ECG variables), the last non-missing value determined prior to the first dosing of BI 1467335 will be defined as baseline.

Time windows are defined in Section 6.1 of the CTP. Adherence to time windows will be checked at the RPM/DBLM.

## 7. PLANNED ANALYSIS

The format of the listings and tables will follow the BI guideline "Reporting of clinical trials and project summaries" (001-MCG-159) (9).

The individual values of all subjects will be listed. Listings will generally be sorted by dose group, ethnicity, subject number and visit (if visit is applicable in the respective listing). AE listings will be sorted by assigned treatment (see [Section 7.8.1](#) below for details). The listings will be contained in Appendix 16.2 (SDL) of the CTR.

The following standard descriptive statistical parameters will be displayed in summary tables of continuous variables:

|        |                                    |
|--------|------------------------------------|
| N      | number of non-missing observations |
| Mean   | arithmetic mean                    |
| SD     | standard deviation                 |
| Min    | minimum                            |
| Median | median                             |
| Max    | maximum                            |

For plasma concentrations as well as for all PK parameters and biomarker parameters, the following descriptive statistics will additionally be calculated:

|       |                                     |
|-------|-------------------------------------|
| CV    | arithmetic coefficient of variation |
| gMean | geometric mean                      |
| gCV   | geometric coefficient of variation  |
| P10   | 10 th percentile         |
| Q1    | 1 st quartile            |
| Q3    | 3 rd quartile            |
| P90   | 90 th percentile         |

The data format for descriptive statistics of plasma concentrations will be identical with the data format of the respective concentrations. The descriptive statistics of PK parameters will be calculated using the individual values with the number of decimal places as provided by the evaluation program. Then the individual values as well as the descriptive statistics will be reported with three significant digits in the CTR.

Tabulations of frequencies for categorical data will include all possible categories and will display the number of observations in a category as well as the percentage (%) relative to the respective treatment. Percentages will be rounded to one decimal place. The category missing will be displayed if and only if there actually are missing values. Percentages will be based on all subjects in the respective subject set whether they have non-missing values or not.

### 7.1 DEMOGRAPHIC AND OTHER BASELINE CHARACTERISTICS

Only descriptive statistics are planned for this section of the CTR.

## **7.2 CONCOMITANT DISEASES AND MEDICATION**

Concomitant diseases will be coded according to the most recent version of MedDRA. Concomitant medication will be coded according to the most recent version of the World Health Organisation – Drug Dictionary.

Only descriptive statistics are planned for this section of the CTR.

A medication will be considered concomitant to a treatment, if it

- is ongoing at the time of first administration of the respective treatment or
- starts within the analysis phase of the respective treatment (see [Section 6.1](#) for a definition of treatments and analysis phases).

## **7.3 TREATMENT COMPLIANCE**

Treatment compliance (%) will be analysed using descriptive statistics and also using frequency tables for categories of treatment compliance. Categories will be defined as <80%, 80% - 100% and >100%.

Any deviations from complete intake will be addressed in the RPM/DBLM (cf. [Section 6.2](#)) and described in the CTR.

## **7.4 PRIMARY ENDPOINTS**

Refer to [Section 7.8.1](#) for a description of the analysis of AEs, and in particular the analysis of the frequency of subjects with drug related AEs, which is the primary endpoint of this trial.

## **7.5 SECONDARY ENDPOINT**

### **7.5.1 Key secondary endpoint**

Not applicable.

### **7.5.2 Secondary endpoints**

The analysis of secondary endpoints will be based on the PKS.

Dose proportionality of secondary endpoints will be evaluated as defined in the CTP, Section 7.3.1, by use of the power model. The assessment of dose proportionality will be performed for Japanese subjects only. 2 type placebo groups, Placebo for Japanese and Total placebo, will be used for dose proportionality analysis. If steady state will already be reached after 14 days of treatment, dose proportionality will also be investigated for  $AUC_{0-24,14}$  and  $AUC_{0-24,28}$  together (and for  $C_{max,14}$  and  $C_{max,28}$  together, respectively) by use of a repeated measurements model.

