3.3.5 Replacement of subjects

In case some subjects of an ethnic cohort do not complete the dose level, the trial clinical monitor together with the trial pharmacokineticist and the trial statistician are to decide whether and how many subjects will be replaced. A replacement subject will be assigned a unique study subject number, and will be assigned to the same treatment as the subject he replaces. There will be no replacement for the subjects removed due to safety reason related to the trial drug.

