7.3.1 Primary analyses

All treated subjects (that is, all subjects who received at least one dose of study drug), will be included in the treated set.

Proprietary confidential information © 2017 Boehringer Ingelheim International GmbH or one or more of its affiliated companies

The primary endpoint will be analysed only descriptively on the treated set. For more details see [Section 7.3.3](#).

The secondary endpoints (refer to [Section 5.5.1.1](#)) will be calculated according to the BI Standard Operating Procedure (SOP) 'Standards and processes for analyses performed within Clinical Pharmacokinetics/Pharmacodynamics' [[001-MCS-36-472](#)].

Plasma concentration data and parameters of a subject will be included in the statistical pharmacokinetic (PK) analyses if they are not flagged for exclusion due to a protocol violation relevant to the evaluation of PK (to be decided no later than in the Report Planning Meeting) or due to PK non-evaluability (as revealed during data analysis, based on the criteria specified below). Exclusion of a subject's data will be documented in the CTR. Relevant protocol violations may be

- Incorrect trial medication taken, i.e. the subject received at least one dose of trial medication the subject was not assigned to
- Incorrect dose of trial medication taken
- Use of restricted medications.

Plasma concentrations and/or parameters of a subject will be considered as non-evaluable, if for example

- the subject experienced emesis that occurred at or before two times median t_{max} of the respective treatment (Median t_{max} is to be determined excluding the subjects experiencing emesis),
- missing samples/concentration data at important phases of PK disposition curve.

The PK parameter analysis set (PKS) includes all subjects in the Treated Set (TS) who provide at least one PK parameter that was not excluded according to the description above. All statistical evaluations of PK parameters will be based on the PKS.

Excluded subjects will be listed with their individual plasma concentrations and individual pharmacokinetic parameters, however, will not be included in descriptive statistics for plasma concentrations, pharmacokinetic parameters or other statistical assessment.

Assessment of dose proportionality

Dose proportionality will be assessed using the pharmacokinetic endpoints AUC_{0-24} , C_{max} , $AUC_{0-24,28}$ and $C_{max,28}$ as specified in [Section 5.5.1.1](#).

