The basic model for the investigation of dose proportionality will be a power model that describes the functional relationship between the dose and PK endpoints.

$$\exp(Y_{ij}) = \alpha' * \exp(X_i)^\beta * \varepsilon'_{ij}$$

The model consists of a regression model applied to log-transformed data. The corresponding ANCOVA model includes the logarithm of the dose as a covariate.

Proprietary confidential information © 2017 Boehringer Ingelheim International GmbH or one or more of its affiliated companies

Together with $\alpha' = \exp(\alpha)$ and $\varepsilon'_{ij} = \exp(\varepsilon_{ij})$, taking natural logarithms converts this model to a linear form as follows:

$$Y_{ij} = \alpha + \beta * X_i + \varepsilon_{ij}$$

where

Y_{ij} logarithm of the pharmacokinetic endpoint for subject j at dose level i;
where $i = 1, 2, 3, j = 1, 2, \dots, 12$;

α intercept parameter;

β slope parameter;

X_i logarithm of dose i;

ε_{ij} random error associated with subject j at dose level i (assumed to be independent and identically normally distributed).

This equation can be fit as a linear regression model.

Based on the estimate for slope parameter (β), a 2-sided 95% CI for the slope will be computed. Perfect dose proportionality would correspond to a slope of 1. The assumption of a linear relationship between the log-transformed pharmacokinetic endpoint and the log-transformed dose will be checked.

Graphical displays

To support the analyses of dose proportionality, linearity graphical representations of the data might be created. These might include (but are not limited to) individual time-courses of trough and 0.5 h, 1 h post-dose plasma concentrations and the (geometric) mean plasma concentration time profiles.

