7.4.3 Pharmacokinetic parameters

No imputation of missing PK parameters will be performed.

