## **6. GENERAL ANALYSIS DEFINITIONS**

### **6.1 TREATMENTS**

For basic study information on treatments to be administered, assignments of dose groups, and selection of doses, cf. Section 4 of the CTP.

Subjects were treated with 3 mg, 6 mg or 10 mg of BI 1467335 (test treatment, T) or placebo (reference treatment, R) once daily over 28 days. Three placebo groups will be defined: Placebo for Japanese, Placebo for Caucasians and Total placebo. Placebo for Japanese will be defined as a pooled group of the Japanese subjects receiving placebo treatment in the three dose groups. Placebo for Caucasians will be defined as the placebo subjects in the 10 mg dose group for Caucasians (which comprises all placebo-treated Caucasian subjects). Total placebo will be defined as one pooled placebo group (i.e. no distinction between dose groups and ethnicity will be made for placebo subjects).

For statistical analysis of AEs, safety laboratory data, vital signs and ECG, the following analysis phases are defined for each subject:

Table 6.1: 1 Flow chart of analysis phases for statistical analyses of AEs, safety laboratory data, vital signs and ECG

| Study analysis phase | Label  | Start (inclusive)                               | End (exclusive)                                    |
|----------------------|--|---|--|
| Screening            | Screening  | Date of informed consent                        | Date/time of first administration of study drug    |
| On-treatment         | Placebo,
3 mg BI for
Japanese,
6 mg BI for
Japanese,
10 mg BI for
Japanese
or 10 mg BI for
Caucasians,
respectively | Date/time of first administration of study drug | 0:00 on day after subject's trial termination date |

CTR Section 15, Appendix 16.1.9.2.8.2 and Appendix 16.1.9.2.8.3 AE displays will present results for the on-treatment phase only.

In CTR Section 15 AE tables (but not in Appendix 16.1.9.2.8.2 and Appendix 16.1.9.2.8.3 AE tables), the following totals will be provided in addition:

- "**Total BI**", defined as the total over all on-treatment phases involving BI, i.e., "3 mg BI for Japanese" + "6 mg BI for Japanese" + "10 mg BI for Japanese" + "10 mg BI for Caucasians"
- "**Total BI for Japanese**", defined as the total over all on-treatment phases involving BI, i.e., "3 mg BI for Japanese" + "6 mg BI for Japanese" + "10 mg BI for Japanese"

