### **Exclusion of PK parameters**

The ADS ADPP contains column variables APEXC and APEXCO indicating inclusion/exclusion (APEXC) of a PK parameter and an analysis flag comment (APEXCO). All analyses based on the PKS are based on PK parameter values which are not flagged for exclusion, i.e. with APEXC equal to "Included".

Exclusion of plasma concentrations

The ADS ADPC (PK concentrations per time-point or per time-interval) contains column variables ACEXC or ACEXCO indicating inclusion/exclusion (ACEXC) of a concentration and an analysis flag comment (ACEXCO). Exclusion of a concentration depends on the analysis flag comment ACEXCO. For example, if ACEXCO is set to "ALL CALC", the value will be excluded for all types of analyses based on concentrations. If ACEXCO is set to "DESC STATS" the value will be excluded from descriptive evaluations per planned time point/time interval. If ACEXCO contains the addition "TIME VIOLATION" or "TIME DEVIATION", the value can be used for further analyses based on actual times. If ACEXCO is set to "HALF LIFE", the value will be excluded from half-life calculation only; the value is included for all other analyses.

Further details are given in 001-MCS-36-472\_RD-01 "Noncompartmental Pharmacokinetic / Pharmacodynamic Analyses of Clinical Studies" (4) and 001-MCS-36-472\_RD-03 "Description of Analytical Transfer Files and PK/PD Data Files" (5).

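### Can the two placebo groups named in SAP 7.5.2 alter the dose-proportionality analysis?

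*SAP*

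**What the plan says.** SAP 7.5.2 bases the secondary endpoints on the PK parameter analysis set (PKS) and refers to Protocol 7.3.1 for the power model. It then says "The assessment of dose proportionality will be performed for Japanese subjects only", and in the next sentence "2 type placebo groups, Placebo for Japanese and Total placebo, will be used for dose proportionality analysis".

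SAP 6.1 defines the groups. Placebo for Japanese pools the Japanese placebo subjects of the three dose groups. For the other group, "Total placebo will be defined as one pooled placebo group (i.e. no distinction between dose groups and ethnicity will be made for placebo subjects".

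Protocol 7.3.1 writes the model as a straight line in log dose for three dose levels, with subjects within a level indexed from 1 to 12. The PKS "includes all subjects in the Treated Set (TS) who provide at least one PK parameter" that has not been excluded. Two further rules apply: "No imputation of missing PK parameters will be performed" (Protocol 7.4.3) and "All analyses based on the PKS are based on PK parameter values which are not flagged for exclusion" (SAP, Exclusion of PK parameters).

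**The concern.** Consecutive sentences in SAP 7.5.2 do not fit together. One restricts the analysis to Japanese subjects. The next assigns it two placebo groups, one of which contains Caucasians. Neither group has a place in a regression on log dose. The index running to 12 per dose level adds to the impression, because 12 is the 9 active plus the 3 placebo subjects in each Japanese dose group.

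The SAP is final and programmers work from it. If someone obeyed the sentence by giving placebo subjects an invented small dose and a small response, the slope would depend on the invention and would no longer estimate dose proportionality.

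A second thought arises in the same section. The trial's title says the Caucasian group is there for comparison, yet the visible secondary analyses contain descriptive statistics and a slope in Japanese subjects only, with no ratio between the two ethnic groups at 10 mg.

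**Working it through.** **Inputs.** Protocol Table 3.1: 1 gives 9 active and 3 placebo subjects in each of four cells: Japanese 3, 6 and 10 mg, and Caucasian 10 mg. Protocol 7.3.1 gives the model and a two-sided 95% interval for the slope. The visible documents give no coefficient of variation (CV), so the CVs below are assumptions.

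**Planned total.** 4 × (9 + 3) = 48, which reproduces Protocol 7.6. Of these, 36 are active and 12 placebo.

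**Size of the named groups.** Placebo for Japanese: 3 × 3 = 9. Total placebo: 4 × 3 = 12, of whom 3 are Caucasian.

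**Can a placebo subject enter the fit?**

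- Covariate: log(0) is minus infinity. The model has three dose levels, none of them placebo, and the plan has no rule for dose zero.
- Response: under Protocol 7.4.2, values below the quantification limit are set to zero in the lag phase and otherwise ignored. A placebo profile should therefore yield a zero or a missing parameter, and neither can be logged.
- Imputation: Protocol 7.4.3 rules it out for PK parameters.
- Zero concentration for placebo: SAP 6.3 provides for this, but only in the ECG exposure-response analysis.

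Usable placebo subjects are therefore 0 of 9 and 0 of 12. The fit uses 3 × 9 = 27 active Japanese subjects as planned. This number is not fixed, since Protocol 3.3.5 leaves open "whether and how many subjects will be replaced".

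**Precision of that fit.** With X = ln 3, ln 6 and ln 10, nine subjects each, the sum of squares about the mean is 6.573. The 95% half-width for the slope is t(0.975; 25 df) × SD / √6.573, with SD = √ln(1 + CV²). At an assumed CV of 40%, SD = 0.385 and the half-width is 2.060 × 0.385 / 2.564 = 0.309. At CVs of 20%, 30% and 60% it is 0.159, 0.236 and 0.445. These values are the same whether or not the placebo sentence is in the SAP.

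**The index to 12.** Twelve values per level would give 36 observations and a half-width of 0.264 at a CV of 40%. That cannot occur, because only the active subjects have values that can be logged. An index range does not create data.

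**What forcing placebo in would do.** Take exact data with slope 1.5 for the 27 active subjects, and add 9 or 12 placebo subjects at placeholder doses and responses between 0.01 and 1. The fitted slope then runs from 1.144 to 3.605, depending on the placeholder. Going from 9 to 12 placebo subjects moves it by at most 3.605 − 3.508 = 0.097. No rule in the plan allows such placeholders.

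**Ethnic ratio at 10 mg, 9 against 9.** Protocol 7.3.5 and SAP 7 already require N, geometric mean and geometric CV for the PK parameters. If these are tabulated by ethnicity, the ratio of the geometric means follows directly, with interval factor exp(t(16 df) × SD × √(2/9)). At an assumed CV of 30% the 95% factor is exp(2.1199 × 0.294 × 0.471) = 1.34, so an observed ratio of 1 has an interval of 0.75 to 1.34. At a CV of 60% it is 0.57 to 1.74.

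**The case for a change.** The strongest case for a change is that a final SAP should not contain an instruction that cannot be carried out. The clash between Total placebo and the restriction to Japanese subjects is plain on the page, does not depend on the log(0) argument, and cannot be blamed on removed text. The placeholder results show that a literal-minded workaround would do real harm. The sentence may also have been meant for another analysis, which would then lack its placebo definition.

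The first part stands: the sentence is wrong as written. The rest does not lead to a change. An analyst who follows the model to which SAP 7.5.2 refers has no covariate value for placebo and would have to invent one against the plan's own rules. The Caucasian placebo subjects raise no separate problem, since no placebo subject enters at all. That another analysis lost its definition is conjecture: SAP 6.1 defines all three placebo groups for general use, Protocol 7.3.3 gives the safety control, and SAP 6.3 covers placebo in the ECG exposure-response analysis.

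One link is inferred. No visible text says outright that placebo samples yield no PK parameter. The conclusion does not need it, because the zero dose alone excludes these subjects.

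For the ethnic ratio, the argument is that fixing contrast and confidence level beforehand gives one agreed estimate, and Protocol 7.2 accepts intervals as estimates of effects. That is a fair preference. But the trial is descriptive and not powered, and with nine per group the interval could not support a claim of similarity. The public copy also lacks Protocol 7.3.2 and 5.5.1.2, and the SAP contents go from 7.5.2 (page 25) to 7.7 (page 28), so the comparison may already be there.

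**Conclusion.** The inconsistency is real but clerical. The protocol's model, the analysis set and the rule against imputation leave a single feasible analysis, the actively treated Japanese subjects (27 planned). The expected effect of the placebo sentence on the slope and its 95% interval is zero, and the index to 12 is a matter of notation. The endpoint is secondary and exploratory, with no hypothesis test attached.

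The ethnic ratio at 10 mg is an optional addition. Nearly the same information follows from the planned geometric means and CVs, provided they are reported by ethnicity, and its absence cannot be established from the public copy.

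The conclusion assumes that analysts fit the model as Protocol 7.3.1 writes it, that the repeated-measurements version in SAP 7.5.2 keeps log dose as its covariate, and that no dose or response values are invented for placebo. The CVs serve only to illustrate precision. No change to the plan is needed.
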